7. DEMOGRAPHIC AND OTHER BASELINE CHARACTERISTICS

Demographic parameters as allowed by local country legislation (eg, age, sex, race, ethnicity) and other baseline characteristics (weight and body mass index, etc) will be summarized for the Safety Population.

Prior medical and surgical history at the enrollment of lead-in studies will be summarized for the Safety Population.

Baseline efficacy parameters MADRS total score and CGI-S score will be summarized by for the Safety Population.

Confidential Page 15 of 40

8. EXTENT OF EXPOSURE AND TREATMENT COMPLIANCE

8.1 Extent of Treatment Exposure

Exposure to open-label lumateperone for the Safety Population will be summarized for treatment duration, calculated as the number of days from the date of the first dose of open-label lumateperone taken to the date of the last dose taken, inclusive. The number and percentage of patients with each treatment duration category will be summarized, respectively.

8.2 Measurement of Treatment Compliance

Dosing compliance for a specified period is defined as the total number of capsules of lumateperone actually taken by a patient during the treatment period divided by the number of capsules of lumateperone that is expected to be taken during the Open-label Treatment Period multiplied by 100.

The total number of capsules actually taken during the treatment period will be calculated from the study drug record. Descriptive statistics for study drug dosing compliance together with compliance category will be summarized for the Safety Population.

8.3 Prior and Concomitant Medication

Prior medication is defined as any medication taken before the date of the first dose of open-label lumateperone. *Prior concomitant medication* is any medication that started before the date of the first dose of open-label lumateperone and stopped or is ongoing after the date of the first dose of open-label lumateperone. *Concomitant* medication is defined as any medication taken on or after the date of the first dose of open-label study drug.

Prior, prior concomitant, and concomitant medication use will be summarized as the number and proportion of patients who received each prior, prior concomitant, and/or concomitant medication within each therapeutic class and preferred term. Multiple medications used by a patient will only be counted once.

Any medication that started after the date of the last dose of open-label lumateperone will not be included in the summary but will be included in the patient data listings.

Confidential Page 16 of 40

9. EFFICACY ANALYSES

The efficacy analyses will be based on patients in the Safety Population with an available baseline efficacy value and at least one postbaseline efficacy assessment during the Open-label Treatment Period. Baseline is defined as the last measurement prior to the first dose of double-blind treatment during the lead-in studies (Studies ITI-007-501 and ITI-007-502).

9.1 MADRS Total Score

Descriptive statistics for the change from baseline to each assessment visit in MADRS total score will be provided for each scheduled visit. Also, the number of patients who achieved remission (MADRS total score ≤ 10) will be provided for each scheduled visit. In addition, the responder rate (response is defined as at least 50% reduction in MADRS total score compared to baseline score) will be provided for each scheduled visit.

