6.6 Changes in the Conduct of the Study

Any amendment to this protocol will be provided by the Sponsor in writing to the Investigator. No protocol amendment may be implemented before it has been approved by the IRB/IEC and competent local authorities (if applicable) and the signature page, signed by the Investigator, has been received by the Sponsor. If the protocol is amended to eliminate or reduce the risk to patients, the amendment may be implemented before IRB/IEC review and approval. However, the IRB/IEC must be informed in writing of such an amendment, and approval must be obtained within reasonable time limits.

Administrative changes, such as changes in study personnel, will be specified in the Study Reference Manual. Administrative changes will not require a protocol amendment.

7. STUDY TREATMENTS

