9. STATISTICAL METHODS

9.1 General Considerations

The statistical analysis plan (SAP) will be finalized prior to database lock and will include a more technical and detailed description of the statistical analyses described in this section. This section is a summary of the planned statistical analyses of important endpoints including primary and key secondary endpoints.

Continuous variables will be summarized using descriptive statistics (number of patients [n], mean, standard deviation [SD], median, minimum, and maximum, unless otherwise stated). Categorical variables will be summarized using frequency counts and percentages.

The baseline for each specific efficacy/safety change-from-baseline analysis endpoint is defined as the last measurement prior to the first dose of study treatment from the lead-in study.

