9.4.4 Efficacy Analyses

The efficacy analyses will be based on patients in the Safety Population with an available baseline efficacy value and at least one postbaseline efficacy assessment during the Open-label Treatment Period.

The efficacy endpoints are change from baseline in MADRS total score and change from baseline in CGI-S score.

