9.4.4.1 MADRS Total Score

A descriptive summary for the change from baseline to each assessment visit in MADRS total score will be provided. Also, the number of patients who achieved remission (MADRS total score ≤ 12) will be provided. In addition, the responder rate (response is defined as at least 50% reduction in MADRS total score compared to baseline score) will be summarized.

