2. INTRODUCTION

This statistical analysis plan (SAP) provides the technical and detailed elaboration of the statistical analyses of the efficacy and safety data as outlined and/or specified in the Protocol Amendment 1 (dated 23 Aug 2021) of Study ITI-007-503.

Study ITI-007-503 ("Study 503") is an international, open-label, multicenter, 6-month study to assess the safety and tolerability of lumateperone as adjunctive therapy in patients with MDD. The Study will be performed at approximately 120 study centers. No *de novo* patients will be enrolled.

Patients who have safely completed the lead-in studies may be eligible to participate in this Open-label Safety Study. Lead-in study completion is defined as a patient who completes the double-blind treatment period (ie, all scheduled visits up to and including Visit 8) of the lead-in study.

The study will be conducted as follows:

- A Screening Period of one day in duration. Potential patients rolling over from the lead-in studies will be evaluated for eligibility during the Screening/Baseline Visit (Visit 1/Day 1) which is the same visit as Visit 8/Day 43 of the lead-in study. Patients who meet all eligibility criteria at the Screening/Baseline Visit (Visit 1/Day 1) will be dispensed lumateperone 42 mg to be self-administered each evening without respect to food.
- A **26-week Open-label Treatment Period** during which patients will self-administer lumateperone, to be taken each evening, without respect to food. Background ADT should also continue as previously prescribed, with no change of dose from the lead-in studies. Patients will attend visits on Weeks 1, 2, 3, 4, 6, 8, 10, 12, 14, 16, 18, 20, 22, 24, and 26. The Open-label Treatment Period will last a total of 26 weeks. A patient will be defined as a treatment completer if the patient completes the Open-label Treatment Period (all scheduled visits up to and including Visit 16/Week 26).
- A 2-week Safety Follow-up Period. A Safety Follow-up visit will occur approximately 2 weeks after completion of the Open-label Treatment Period or after the Early Termination (ET) Visit. Any ongoing AEs at the Safety Follow-up Visit must be followed until resolution, until the AE stabilizes, until it is determined to be not clinically significant, or until the patient is lost to follow-up.

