16. CHANGES TO ANALYSES SPECIFIED IN PROTOCOL

No major changes made to the analyses specified in the latest protocol amendment for Study ITI-007-503 Amendment 1 (dated 23 Aug 2021).

Confidential Page 38 of 40

17. REFERENCES

None.

Confidential Page 39 of 40

18. APPENDICES

None.

Confidential Page 40 of 40

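### Remission is a MADRS total of 12 or less in Protocol 9.4.4.1 but 10 or less in SAP 9.1, and SAP 16 does not list the difference

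*SAP*

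**What the plan says.** Protocol 9.4.4.1 plans that "the number of patients who achieved remission (MADRS total score ≤ 12) will be provided". SAP 9.1 plans that "the number of patients who achieved remission (MADRS total score ≤ 10) will be provided for each scheduled visit". Both are current body text.

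The SAP presents itself in Section 2 as a "technical and detailed elaboration of the statistical analyses of the efficacy and safety data as outlined and/or specified in the Protocol Amendment 1". The date it gives for that amendment, 23 Aug 2021, is also the date on the protocol pages. Protocol 9.1 describes the SAP's task in similar terms: it "will include a more technical and detailed description of the statistical analyses described in this section". SAP 16, the section reserved for departures from the protocol, says "No major changes made to the analyses specified in the latest protocol amendment" and has no individual entries.

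The companion responder definition agrees in the two documents: "response is defined as at least 50% reduction in MADRS total score compared to baseline score".

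**The concern.** The documents give two cut-offs for remission on the same scale in the same study. Changing a cut-off does not add technical detail to an analysis; it redefines the outcome. An out-of-date SAP does not explain the gap, since the SAP names the protocol version in hand, and neither document gives a reason.

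The reported number of remitters therefore depends on which document is followed. Someone relying on SAP 16 would not learn that SAP 9.1 departs from the protocol, and someone reading the results against the protocol would take the count to be based on 12 or less.

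Documentation matters more here because the study is open-label and the SAP is dated 24 Jun 2024, after the 30 Apr 2024 cut-off of the interim analysis in its own Section 12. Nothing in the documents suggests a data-driven choice, and the stricter cut-off can only lower the count. But a change log exists to explain a change of this kind.

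**Working it through.** The plan states no remission rate, so there is no figure to reproduce. The check is a comparison of texts, followed by an illustration of size.

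**Texts side by side**

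| Item | Protocol 9.4.4.1 | SAP 9.1 |
|---|---|---|
| Remission | MADRS total ≤ 12 | MADRS total ≤ 10 |
| Response | reduction of at least 50% from baseline | the same |
| Visits for the remission count | not stated | each scheduled visit |

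Only the remission cut-off conflicts. The by-visit wording in the SAP is a legitimate elaboration.

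**What follows with certainty**

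1. The MADRS total runs from 0 to 60 (Protocol 8.1.1) and is a whole number if each of its ten items is scored in whole points. The two rules then disagree only for totals of 11 and 12.
2. Remission rate at ≤ 12 minus remission rate at ≤ 10 = P(total is 11 or 12), which cannot be negative. The SAP count can never exceed the protocol count.
3. The Schedule of Evaluations has MADRS at ten post-baseline visits in the Open-label Treatment Period: Weeks 1, 2, 3, 4, 8, 12, 16, 20, 24 and 26.

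**Illustration of size (all means and SDs are assumptions)**

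The documents give no on-treatment MADRS mean or SD. Take a mean of 14 and an SD of 8.

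- *Beta-binomial on 0–60, matched to that mean and SD.* p = 14/60 = 0.2333. Variance ratio = 64/(60 × 0.2333 × 0.7667) = 5.963. Intraclass correlation = (5.963 − 1)/59 = 0.0841. a + b = 1/0.0841 − 1 ≈ 10.89, so a ≈ 2.54 and b ≈ 8.35. P(≤ 12) = 48.0%, P(≤ 10) = 38.1%, gap 10.0 points from unrounded values.
- *Normal with continuity correction.* Φ((12.5 − 14)/8) − Φ((10.5 − 14)/8) = Φ(−0.1875) − Φ(−0.4375) = 42.6% − 33.1% = 9.5 points.
- *Gamma, same cut points.* 50.0% − 38.8% = 11.2 points.

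**Range.** Means 6 to 25 and SDs 6 to 12, both in steps of 0.5 (39 × 13 = 507 combinations per model):

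| Model | Smallest gap (points) | Largest gap (points) |
|---|---|---|
| Beta-binomial | 0.97 (mean 25, SD 6) | 13.3 (mean 13, SD 6) |
| Normal | 1.1 (mean 25, SD 6) | 13.2 (mean 11.5, SD 6) |
| Gamma | 0.5 (mean 25, SD 6) | 14.4 (mean 13.5, SD 6) |

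With the mean held at 14, raising the SD from 6 to 12 lowers the gap from about 13 to 6 points (beta-binomial), 12 to 6.5 (normal) and 14 to 7 (gamma).

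A separate check with a normal distribution truncated to 0–60, means 8 to 20 and SDs 7 to 9, gives gaps of 5.5 to 11.8 points. That would be 42 to 89 patients if all of the approximately 760 planned patients were assessed.

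**The case against.** The strongest reply concerns weight. Remission is not a named endpoint: "The efficacy endpoints are change from baseline in MADRS total score and change from baseline in CGI-S score". It is an untested count in a single-arm study whose primary objective is safety and whose sample size has no power basis. No eligibility, treatment or safety rule uses it. The SAP cut-off is the stricter one and cannot flatter the drug, and the count at 12 or less can be derived later from the same scores. All of this stands, and it limits the severity.

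SAP 16 denies only major changes, and a sponsor may call this one minor, so its sentence is not false. It is still incomplete on this point: a changed outcome definition has no entry and no reason anywhere in the SAP.

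Two smaller points also stand. The protocol does not say that remission is counted by visit, so the by-visit count comes from SAP 9.1 alone. And ten is the number of on-treatment post-baseline visits, not necessarily of affected tabulations. MADRS is also scheduled at Visit 1 and at Safety Follow-up, and the MADRS window table is not legible in the text available, so the visits to be tabulated cannot be confirmed.

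Finally, the size rests wholly on assumed distributions, and the range is wide enough to run from negligible to noticeable. The untruncated normal model also puts some probability below zero when the mean is low and the SD high. The contradiction itself depends on none of these assumptions.

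**Conclusion.** The point holds. The two documents define remission differently, and SAP 16 does not disclose it. It is certain that totals of 11 and 12 are reclassified and that the SAP count is equal or lower. The size is not known from the documents: about 10 fewer remitters per 100 assessed under one assumed distribution (mean 14, SD 8), and 0.5 to 14.4 percentage points over the assumed grid and three models.

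The change analyses in MADRS and CGI-S and the response definition are unaffected, and no test, error rate or power is involved. This should be fixed, but it does not threaten the study's main conclusions.

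**What to change.** Correct it in the SAP, in one of two ways:

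- change the cut-off in SAP 9.1 to the protocol's 12 or less; or
- keep 10 or less, also report the count at 12 or less labelled as the protocol definition, and enter the change and its reason in SAP 16.

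The first costs one sentence. The second adds an SAP 16 entry and one extra remission line at each tabulated visit. Neither needs new data, and neither alters the protocol. Changing the protocol's cut-off instead would presumably take an amendment, and Protocol 6.6 says that "No protocol amendment may be implemented before it has been approved by the IRB/IEC", so the SAP route is simpler.

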9.2 CGI-S Score

A descriptive summary for the change from baseline to each assessment visit in CGI-S score will be provided for each scheduled visit.

Confidential Page 17 of 40

10. SAFETY ANALYSES

Safety analyses will be performed using the Safety Population. The safety parameters will include AEs, clinical laboratory, vital signs, ECG, and EPS (AIMS, BARS, and SAS) and C-SSRS scales. Baseline is defined as the last measurement prior to the first dose of double-blind treatment during the lead-in studies (Studies ITI-007-501 and ITI-007-502).

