10.3 Vital Signs

Descriptive statistics for vital signs (eg, supine pulse rate, supine systolic and diastolic BP, body weight) values at baseline and changes from baseline values at each assessment visit, and at the end of the Open-label Treatment Period will be presented.

Vital sign values will be considered PCS if they meet the criteria for both the observed value and the change from baseline value listed in Table 10-4. The number and percentage of patients with PCS postbaseline vital sign values during Open-label Treatment Period will be tabulated for the Safety Population. The percentages will be calculated relative to the number of patients with an available baseline value and at least 1 postbaseline assessment. The numerator will be the total

Confidential Page 22 of 40

number of patients with an available baseline value and at least 1 PCS postbaseline vital sign value. A supportive listing of patients with PCS postbaseline values will be provided and will include the PID number and baseline and postbaseline values for each patient. A listing of all AEs for patients with PCS vital sign values will also be provided.

Table 10-4: Criteria for Potentially Clinically Significant Vital Signs

Vital Sion Danameter mit	Elaa	Criteria ^a					
Vital Sign Parameter, unit	Flag	Observed Value	Change From Baseline				
Supine Systolic blood pressure, mmHg	High	≥ 180	Increase of ≥ 20				
Supine Systone blood pressure, mining	Low	≤ 90	Decrease of ≥ 20				
Suning Digetalia blood procesure, mmHg	High	≥ 105	Increase of ≥ 15				
Supine Diastolic blood pressure, mmHg	Low	≤ 50	Decrease of ≥ 15				
Supine Pulse rate, bpm	High	≥ 120	Increase of ≥ 15				
Supine Fuise rate, opin	Low	≤ 50	Decrease of ≥ 15				
Waighth	High	_	Increase of ≥ 7%				
Weight ^b	Low	_	Decrease of ≥ 7%				

bpm = beats per minute.

The number and percentage of patients with orthostatic hypotension during the Open-label Treatment Period will be provided for the Safety Population. Orthostatic hypotension is defined as a reduction of ≥ 20 mm Hg in SBP or a reduction of ≥ 10 mm Hg in DBP while changing from the supine to standing position. A supportive listing of patients with orthostatic hypotension during the Open-label Treatment Period and Safety Follow-up Period will be provided. A listing of all AEs occurring in patients who experienced orthostatic hypotension will also be provided.

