10.4 Electrocardiograms

Descriptive statistics for ECG parameters (eg, ventricular heart rate, QTc interval, QRS interval) at baseline and changes from baseline values at each assessment visit, and at the end of the Openlabel Treatment Period will be summarized.

ECG parameter values will be considered PCS if they meet the criteria listed in Table 10-5. The number and percentage of patients with PCS postbaseline values during Open-label Treatment Period will be tabulated for the Safety Population. The percentages will be calculated relative to the number of patients with baseline value (for criteria involving change from baseline) or non-PCS baseline value (for criteria not involving change from baseline), and at least 1 assessment during the open-label treatment period. The numerator will be the total number of patients out of those included in the denominator and with at least 1 PCS value during the Open-label Treatment Period. A supportive listing for all patients with PCS values will be provided, which will include the PID number and baseline and postbaseline ECG values for each patient. A listing of all AEs for patients with PCS ECG values will also be provided.

Confidential Page 23 of 40

^a A postbaseline value will be considered potentially clinically significant if it meets both criterion value and change from baseline.

b Weight change is relative to baseline.

Table 10-5: Criteria for Potentially Clinically Significant Electrocardiographic Values

D	Criteria ^a							
Parameter, unit	Value	Change from Baseline						
QRS duration, msec	≥ 150	_						
PR interval, msec	≥ 250	_						
QTcB, msec	≥ 480	_						
QTcB, msec	≥ 500	_						
QTcF, msec	≥ 480	_						
QTcF, msec	≥ 500	_						
QTcB, msec	_	> 30 and ≤ 60						
QTcB, msec	_	Increase of > 60						
QTcF, msec	_	> 30 and ≤ 60						
QTcF, msec	_	Increase of > 60						

PCS = potentially clinically significant; QTc = corrected QT interval; QTcB = QT interval/(RR)½; QTcF = QT interval/(RR)½.

Confidential Page 24 of 40

^a A post-baseline value will be considered potentially clinically significant if it meets the criterion value or the change from baseline value.

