10.5.4 Columbia-Suicide Severity Rating Scale (C-SSRS)

The number and percentage of patients with suicidal ideation or suicidal behavior as recorded on the C-SSRS will be tabulated for lifetime history (assessed at the enrollment of lead-in studies), baseline, Open-label Treatment Period, and Safety Follow-up for the Safety Population. Baseline of C-SSRS for each patient is defined as the last non-missing 'since last visit' assessment before the first dose of study treatment during the lead-in studies. The distribution of responses for the most severe suicidal ideation and most severe suicidal behavior will be presented.

The severity of suicidal ideation will be presented in the following order:

- Wish to be dead
- Non-specific active suicidal thoughts
- Active suicidal ideation with any methods (not plan) without intent to act
- Active suicidal ideation with some intent to act, without specific plan
- Active suicidal ideation with specific plan and intent

The severity of suicidal behavior will be presented in the following order:

- Preparatory acts or behavior
- Aborted attempt
- Interrupted attempt

Confidential Page 25 of 40

- Actual attempt
- Completed Suicide (for Open-label Treatment Period and for Safety Follow-up only)

For each analysis period (lifetime, baseline, Open-label Treatment Period, and safety follow-up), each patient will be counted only once for suicidal ideation and for suicidal behavior, based on the most severe suicidal ideation and the most severe suicidal behavior reported during each specific period. A listing of patients with suicidal ideation or suicidal behavior will be provided. A listing of all AEs for patients with suicidal ideation or suicidal behavior will also be provided.

In addition, the number and percentage of patients with the following emergence of suicidal ideation or of suicidal behavior during the Open-label Treatment Period will be tabulated for the Safety Population:

- Emergence of suicidal ideation (no suicidal ideation at Baseline, and any type of suicidal ideation during Open-label Treatment Period)
- Emergence of serious suicidal ideation (no suicidal ideation at Baseline, and any serious suicidal ideation [Active suicidal ideation with specific plan and intent, or Active suicidal ideation with some intent to act, without specific plan] during Open-label Treatment Period)

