- Worsening of suicidal ideation (most severe suicidal ideation during Open-label Treatment Period was more severe than it was at Baseline)
- Emergence of suicidal behavior (no suicidal behavior at Baseline, and any type of suicidal behavior during Open-label Treatment Period).

Confidential Page 26 of 40

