15.2 Repeated or Unscheduled Assessments of Safety Parameters

For visits with repeated or unscheduled assessments of laboratory parameters, the non-missing values of the scheduled assessment will be used for summary statistics. If the scheduled assessments are missing, the last value from repeated or unscheduled assessments within the analysis window will be used for the visit. If repeated or unscheduled AIMS, BARS, SAS, vital signs or ECGs occur, apply the time-window rule and select the last non-missing values for each visit or endpoint.

All assessments during the Open-label Treatment Period will be included in PCS value determination and will be presented in the data listings.

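### For patients who start lumateperone at open-label entry, the only analysis baseline is not their last pre-drug value; add Visit 1/Day 1 as a supplementary baseline

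*SAP*

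**What the plan says.** Protocol 9.1 sets one baseline for every change-from-baseline endpoint, "defined as the last measurement prior to the first dose of study treatment from the lead-in study". The opening text of SAP 9 (efficacy) and SAP 10 (safety) repeats it: "Baseline is defined as the last measurement prior to the first dose of double-blind treatment during the lead-in studies". SAP 10.5.4 does the same for suicidality: "Baseline of C-SSRS for each patient is defined as the last non-missing 'since last visit' assessment before the first dose". No planned analysis takes Visit 1/Day 1 as its reference. Protocol 8.2.4 calls the lead-in Day 43 laboratory tests the Screening/Baseline tests, but that is a visit label.

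The rules that depend on this baseline are:

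- **Weight (SAP 10.3, Table 10-4):** a change of 7% or more, with no observed-value criterion; "Weight change is relative to baseline".
- **QTc (SAP 10.4, Table 10-5):** increases of more than 30 up to 60 msec, and of more than 60 msec.
- **Laboratory PCS (SAP 10.2) and absolute ECG PCS (SAP 10.4: QRS, PR, QTc of 480 or 500 msec and above):** percentages only among patients not PCS at baseline. Laboratory shift tables run from baseline to the end of treatment.
- **C-SSRS (SAP 10.5.4):** emergence requires no ideation at baseline, including for the serious category: "Emergence of serious suicidal ideation (no suicidal ideation at Baseline, and any serious suicidal ideation". Worsening requires that the "most severe suicidal ideation during Open-label Treatment Period was more severe than it was at Baseline".
- **MADRS and CGI-S (SAP 9.1, 9.2):** change at each visit, and MADRS response as a 50% fall.

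SAP 15.2 adds that "All assessments during the Open-label Treatment Period will be included in PCS value determination", so one qualifying visit is enough.

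**The concern.** Protocol 6.2.1 says that the study lets lead-in participants either begin lumateperone or carry on with it. Visit 1/Day 1 is the same visit as lead-in Day 43, and drug is dispensed there for evening self-administration (Protocol 6.1). For a starter, the Visit 1 assessments are therefore the last values before any lumateperone. The planned baseline lies about six weeks earlier, and change from it mixes lead-in change with change on the drug.

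The primary objective is the safety of open-label lumateperone. A starter's weight or QTc rise that arose in the lead-in and persists would be reported as an open-label finding. A real rise on the drug could be masked by an opposite lead-in change. Patient-level categories cannot be corrected afterwards from summary tables. A mean change since Day 1 might be approximated by subtraction if a Day 1 row is tabulated.

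**Working it through.** There is no design figure to reproduce: the sample size is a feasibility number and the analyses are descriptive.

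**1. Timing.** Take the first lead-in dose on lead-in Day 1 (an assumption). Open-label Day 1 is lead-in Day 43, so the lead-in contributes 43 - 1 = 42 days. With d days since open-label Day 1, the lead-in share of the interval is 42/(42 + d):

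- Week 1: 42/49 = 86%
- Week 4: 42/70 = 60%
- Week 8: 42/98 = 43%
- Week 26: 42/224 = 19%

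**2. The rules applied to hypothetical starters** (lead-in baseline, then Day 1, then an open-label visit):

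| Measure | Values | From lead-in baseline | From Day 1 |
|---|---|---|---|
| Weight, kg | 80, 84, 86 | +7.5%, flagged | +2.4%, not flagged |
| Weight, kg | 80, 75, 81 | +1.3%, not flagged | +8.0%, flagged |
| QTcF, msec | 400, 440, 465 | +65, over 60 | +25, no category |
| QTcF, msec | 420, 395, 457 | +37, over 30 | +62, over 60 |
| MADRS | 30, 18, 14 | -53%, responder | -22%, non-responder |
| MADRS | 24, 36, 18 | -25%, non-responder | -50%, responder |

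Both directions occur for each measure.

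**3. Baseline-status rules.**

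- A laboratory value PCS before the lead-in, normal at Day 1 and PCS at Week 8 is outside both numerator and denominator. The shift table covers only the end of treatment. Absolute ECG criteria behave the same way.
- Ideation before the lead-in, none at Day 1, and the same level again on drug is neither emergence nor worsening.
- No ideation before the lead-in, item 2 at Day 1 and item 2 on drug counts as emergence, although it was present before the drug.
- Items 1-3 at baseline and item 4 or 5 on drug counts as worsening but never as emergence of serious ideation. This holds from either baseline, so a new baseline alone does not cure it.

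**4. Illustrative size for weight, starters only.** All inputs are assumed. Lead-in change L is normal, mean 0, SD 2.5%. Open-label change O is an independent random walk from 0 at Day 1, reaching SD 5% at Week 26 and observed at the 15 scheduled visits. Flag A is L + max O at or above 7; flag B is max O at or above 7. Simulation gives:

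- P(A) = 16.7%, P(B) = 12.2%, both 9.2%.
- Flagged only by the lead-in baseline: 16.7 - 9.2 = 7.5 per 100 starters, 45% of A.
- Flagged only by Day 1: 12.2 - 9.2 = 3.0 per 100, 25% of B.
- Of the 7.5, 58% still gained at least 5% after Day 1 and 77% at least 4%.
- Already at 7% on Day 1: about 0.24 per 100, or 0.24/16.7 = 1.4% of all flags.

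Over SDs of 1.5-3.5% (lead-in) and 4-6% (open-label), A runs from 7.6% to 25.4% and B from 5.8% to 18.9%. The A-only share of A is 20-74% and the B-only share of B is 14-34%. The near-threshold fraction also depends on the SDs: the 58% falls below one half when the lead-in SD is 3.5%.

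**The case against.** The baseline is a deliberate choice, stated consistently in four places. Showing that improvement is maintained needs a reference from before that improvement, and for continuers it is the only pre-drug value. The study is descriptive, with no test to bias. All of this stands, so a reader who infers that the baseline is wrong, or should be replaced by Day 1, goes further than the documents allow.

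The main safety outputs are untouched. TEAEs, SAEs and AEs leading to withdrawal do not use this baseline; nor do MADRS remission, orthostatic hypotension and the most-severe C-SSRS tabulations. Blood pressure and pulse PCS also need an extreme observed value, so they are less exposed. Listings show PCS and C-SSRS cases individually. It would therefore be wrong to infer that safety cases vanish from the report; what is affected is the categorical percentages.

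A reader might also take the 45% as the share of weight flags that are false. It is not. In the base case most of those patients gained 5% or more on drug and merely crossed the threshold with help from the lead-in; very few were already at 7% on Day 1. The figure illustrates reclassification around a cut-off, on assumed SDs.

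Finally, a Day 1 baseline has its own weaknesses. The Day 1 C-SSRS looks back only to the previous lead-in visit, in patients selected low on suicidality, so it would tend to raise emergence counts.

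**Conclusion.** The point holds as a cheap improvement. For starters, the single planned baseline is not the last pre-drug value, and the SAP's own rules then allow misclassification in both directions. That conclusion needs only Protocol 6.2.1, the visit calendar and the rules cited above.

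Its size is unknown. The documents give no lead-in allocation, no share of starters and no SD of change, so no effect on Safety Population percentages can be stated. The weight figures are illustrative only. The visit-window tables in SAP 15.1 are not in the text available, so how Day 1 values are tabulated could not be checked.

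It might be inferred from 'treatment group' in SAP 10.1 and 10.2 that a split by lead-in arm is already planned. The term is never defined, and SAP 5 drops it from the disposition text that Protocol 9.4.1 keeps, so it may be leftover wording.

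**What to change.** Keep the lead-in baseline. In SAP 9, 10 and 10.5.4:

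1. Add a supplementary open-label baseline: the last value before the first open-label dose (Visit 1/Day 1).
2. Report from both baselines: 7% weight change, QTc change categories, laboratory PCS, absolute ECG PCS, laboratory shifts, C-SSRS emergence and worsening, and MADRS/CGI-S change. Other tables can stay on one baseline.
3. Show these by lead-in treatment (starters, continuers, total) once lead-in codes are available, and say whether that applies at the SAP 12 interim analysis.
4. For serious ideation, also tabulate patients with no item 4 or 5 at the relevant baseline and item 4 or 5 during open-label treatment.
5. State the cautions. Day 1 is already on drug for continuers. Day 1 C-SSRS is a short look-back in a sample selected low. Starters and continuers are both selected lead-in completers, so the split is descriptive.

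For the caution on selection, reconcile the entry rule: Protocol 6.3.2 excludes C-SSRS items 4 'or' 5, the synopsis items 4 'and' 5.

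As a separate minor query, define or delete 'treatment group' in SAP 10.1 and 10.2.

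Cost: SAP wording and extra columns in a limited set of tables. Visit 1 values are already scheduled, and patients keep their lead-in ID (Protocol 7.4). The downsides are more tables, and lead-in codes that may not be available at the interim analysis.
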